### **10 CLINICAL MONITORING PLAN**

The detailed clinical monitoring plan has been developed and is available from the Coordinating Center upon request.

## 11. TIMELINE AND ENROLLMENT

### 11.1 Timeline

### 11.2 Screening & Enrollment

Enrollment at each site will be continuously monitored by the site investigator and the principal investigator. Each site will be expected to maintain a screening log including all participants who meet all eligibility criteria at that site. A standardized screening log will be provided to each site via RedCap Cloud—thus allowing for continuous updating of the screening log and will allow capture of all screening failures.

Enrollment will be competitive (i.e. without specific enrollment caps). Number of enrollments at each site will be shared with all sites on a monthly basis. Sites will be expected to complete all elements of the online CRF within 48-hours of each time point. In the case that a site continuously underperforms despite troubleshooting and feedback, the steering committee will evaluate whether enrollment will continue at that site.

## **12. FUNDING**

Funding for the present trial is provided by the Good Ventures Foundation (<http://www.goodventures.org/>). The funding agency will have no role in the design and conduct of the study, collection, management, analysis, and interpretation of the data, preparation, review, or approval of the manuscript, or the decision to submit the manuscript for publication.

## **13. PUBLICATION**

The manuscript will adhere to the CONSORT guidelines. The principal investigator will be responsible for assigning authorship position and will follow authorship guidelines from the International Committee of Medical Journal Editors. At a minimum, all members of the Steering Committee and all site Principal Investigators (for sites enrolling at least 10 participants) will be included in the primary author list. The main results will be presented at an international conference. The trial results will be shared with participating sites and via press releases but not directly with the participants.

## **14. DATA SHARING**

Six months after the publication of the last results, all de-identified individual participant data will be made available for data sharing. Procedures, including re-coding of key variables, will be put in place to allow for complete de-identification of the data. All relevant trial-related documents, including the protocol, data dictionary, and the main statistical code, will be shared along with the data. There will be no predetermined end date for the data sharing. Data will be available for any research purpose to all interested parties who have approval from an independent ethics review committee and who have a methodological sound proposal as determined by the steering committee of the current trial. Interested parties will be able to request the data by contacting the principal investigator. Authorship of publications emerging from the shared data will follow standard authorship guidelines from the International Committee of Medical Journal Editors and might or might not include authors from the steering committee depending on the nature of their involvement.

## **15. TASKS AND RESPONSIBILITIES**

Principal investigator and sponsor: Overall responsibility for protocol development, funding, budget overview, data dictionary development, ethical approval, trial registration, daily management, trial oversight and collection of adverse events, contact to the pharmacy, contact to Good Clinical Practice monitoring unit and the data and safety monitoring board, assessment of overall recruitments, potential recruitment of additional sites, data analysis, and dissemination and presentation of results.

Steering committee: Protocol development, funding, budget overview, data dictionary development, trial oversight, dissemination of results, responsibilities as principal investigator for short time periods.

Site investigators: Responsible for site-specific enrollment, evaluation of eligible patients not included, education of personnel at participating sites, reporting of site-specific issues or challenges to the principal investigator, participant consent for data collection, collecting and reporting data regarding adverse drug events.

Clinical team: Administration of the study drug, participant consent for data collection.

## Appendices

### Appendix 1: Abbreviations

ICH.....	International Conference on Harmonization
SPIRIT.....	Standard Protocol Items: Recommendations for Interventional Trials
ACT.....	Ascorbic Acid, Corticosteroids, and Thiamine
ESRD.....	End Stage Renal Disease
SOFA.....	Sequential Organ Failure Assessment
IND.....	Investigational New Drug
FDA.....	Food and Drug Administration
ICU.....	Intensive Care Unit
SaO 2 .....	Oxygen Saturation
FiO 2 .....	Fraction of Inspired Oxygen
GCS.....	Glasgow Coma Scale
UOP.....	Urine Output
RRT.....	Renal Replacement Therapy
CAM.....	Confusion Assessment Method
NCHS.....	National Center for Health Statistics
NDI.....	National Death Index
AKI.....	Acute Kidney Injury
SD.....	standard deviation
CRF.....	Case Report Form
BIDMC.....	Beth Israel Deaconess Medical Center (Coordinating Center)
IRB.....	Institutional Review Board
DSMB.....	Data Safety and Monitoring Board

Appendix 2: CAM-ICU Form

### CAM-ICU Worksheet

Feature 1: Acute Onset or Fluctuating Course	Score	Check here if Present		

Is the pt different than his/her baseline mental status?
 
OR
 
Has the patient had any fluctuation in mental status in the past 24 hours as evidenced by fluctuation on a sedation scale (i.e., RASS), GCS, or previous delirium assessment?
	Either question Yes →			
Feature 2: Inattention				

Letters Attention Test (See training manual for alternate Pictures)
 
Directions: Say to the patient, "I am going to read you a series of 10 letters. Whenever you hear the letter 'A,' indicate by squeezing my hand." Read letters from the following letter list in a normal tone 3 seconds apart.
 
S A V E A H A A R T
 
Errors are counted when patient fails to squeeze on the letter "A" and when the patient squeezes on any letter other than "A."
			Number of Errors >2 →	
Feature 3: Altered Level of Consciousness				

Present if the Actual RASS score is anything other than alert and calm (zero)
	RASS anything other than zero →			
Feature 4: Disorganized Thinking				

Yes/No Questions (See training manual for alternate set of questions)
 
 
1. Will a stone float on water?
 
2. Are there fish in the sea?
 
3. Does one pound weigh more than two pounds?
 
4. Can you use a hammer to pound a nail?
 
 
Errors are counted when the patient incorrectly answers a question.
 
Command                      Say to patient: "Hold up this many fingers" (Hold 2 fingers in front of patient) "Now do the same thing with the other hand" (Do not repeat number of fingers) *If pt is unable to move both arms, for 2nd part of command ask patient to "Add one more finger"
 
An error is counted if patient is unable to complete the entire command.
			Combined number of errors >1 →	
Overall CAM-ICU				
Feature 1 plus 2 and either 3 or 4 present = CAM-ICU positive	Criteria Met →	 CAM-ICU Positive (Delirium Present)		
	Criteria Not Met →	 CAM-ICU Negative (No Delirium)		

Copyright © 2002, E. [name], MPH and Vanderbilt University, all rights reserved

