## 5.3 Additional Secondary Outcomes

### 5.3.1 Additional secondary outcomes

Additional secondary outcomes will include length of ICU stay, length of hospital stay, ventilator-free days over the first 7-days after enrollment, shock-free days over the first 7-days after enrollment,

and the incidence of delirium on day #3 of the ICU stay (as assessed using the Confusion Assessment Method [CAM-ICU] system). Sites at which the CAM-ICU is performed daily as part of standard-of-care should assess whether delirium occurs on any day during the initial ICU stay. See Appendix #2.

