### 6.2.4 Additional Secondary Analyses

Both ICU and hospital length of stay will be compared using Wilcoxon Rank Sum tests. Ventilator and shock free days over the first 7-days after enrollment will likewise be compared using the Wilcoxon Rank Sum given that the data will likely be not normally distributed. In these latter two analyses, patients who expire prior to 7-days will be assessed to have 0 ventilator or shock free days if they had died while on a ventilator or vasopressor respectively. The incidence of delirium will be compared using the Fisher's exact test. For the quality-of-life outcome (i.e. 90-day SF-36), the primary analysis will only include patients with available data. As a secondary analysis, multiple imputation will be used to estimate SF-36 scores in all patients not known to be dead at 90 -days.

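### As printed, the CAM-ICU worksheet scores a newly comatose or deeply sedated patient as delirious, so an arm difference in unresponsiveness could appear as a difference in delirium

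*Protocol*

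**What the plan says.** Protocol 5.3.1 lists, among the additional secondary outcomes, "and the incidence of delirium on day #3 of the ICU stay", to be judged with the CAM-ICU. Sites that already perform the CAM-ICU daily "should assess whether delirium occurs on any day during the initial ICU stay". Readers are referred to Appendix 2 for the form.

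The Appendix 2 worksheet has four features:

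- **Feature 1** is met by a yes to either of two questions, the first being "Is the pt different than his/her baseline mental status". The second asks about fluctuation in the past 24 hours.
- **Feature 2** has the assessor read out ten letters (S A V E A H A A R T), with the patient to squeeze a hand at each A. The scoring rule is: "Errors are counted when patient fails to squeeze on the letter 'A' and when the patient squeezes on any letter other than 'A". The feature is met at "Number of Errors >2".
- **Feature 3** reads "Present if the Actual RASS score is anything other than alert and calm (zero"; no lower limit of RASS is printed.
- **Feature 4** tests disorganized thinking.

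The result is positive when Features 1 and 2 are both met together with 3 or 4. Only two results are printed, positive and negative.

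The analysis is a single sentence in Protocol 6.2.4: "The incidence of delirium will be compared using the Fisher's exact test". The SAP repeats the same outcome definition, worksheet and analysis sentence.

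**The concern.** The worksheet's scoring rule does not separate a patient who attends poorly from one who cannot respond at all. Failing to squeeze counts as an error whatever the reason. Unresponsive patients can be expected in a vasopressor-dependent septic population: the trial's own SOFA table runs down to a Glasgow Coma Scale below 6, and ventilator-free days are an outcome.

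The regimen is expected to change the course of illness, so the share of patients in coma or under deep sedation at assessment could differ by arm. If such patients are counted as delirious, that difference enters the delirium rate even when delirium among testable patients is the same in both arms. The error can run in either direction. Protocol 8.1.2 names delirium among the hypothetical risks of hydrocortisone, so a false signal either way would be unwelcome.

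**Working it through.** **Step 1. Apply the printed rule to a newly unresponsive patient.**

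- Feature 1: mental status differs from baseline, so it is met.
- Feature 2: S-**A**-V-E-**A**-H-**A**-**A**-R-T contains 4 As. With no squeezes there are 4 missed As and 0 false squeezes, so 4 errors. Since 4 > 2, it is met.
- Feature 3: RASS is not zero, so it is met. Feature 4 is not needed.
- Result: 1 and 2 and 3, so CAM-ICU positive.

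Two counter-checks limit the claim. A lightly sedated patient (RASS -2) who makes no letter errors fails Feature 2 and scores negative. An unresponsive patient with no change or fluctuation from baseline fails Feature 1 and also scores negative.

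**Step 2. Check the Fisher calculation.** The documents state no delirium rate, effect or power, so there is no delirium figure to reproduce. The same exact calculation was tried on two figures in Protocol 6.1. Renal failure of 30% versus 55% at 100 per arm gives 93.9% power (stated 94%). Mortality of 20% versus 40% at 91 per arm gives 80.8% (stated 80% with 182 participants).

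**Step 3. Size of the effect, on assumed rates.** From the documents: 100 per arm, two-sided 0.05, Fisher's exact test. Assumed: everyone is alive and in the ICU at assessment; delirium among responsive patients is *d* in both arms; the unresponsive share is *c*. Under the printed rule the scored rate is

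scored = *c* + (1 - *c*) x *d*.

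For *d* = 0.40 with *c* = 0.15 (active) and 0.25 (placebo): 0.15 + 0.85 x 0.40 = 0.49, and 0.25 + 0.75 x 0.40 = 0.55.

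| Unresponsive, active vs placebo | d | Scored delirium | Rejects, as printed | Rejects, unresponsive excluded |
|---|---|---|---|---|
| 20% vs 20% | 30% | 44.0% vs 44.0% | 3.9% | 3.3% |
| 20% vs 20% | 40% | 52.0% vs 52.0% | 4.0% | 3.2% |
| 20% vs 20% | 50% | 60.0% vs 60.0% | 3.6% | 3.2% |
| 15% vs 25% | 30% | 40.5% vs 47.5% | 14.3% | 4.1% |
| 15% vs 25% | 40% | 49.0% vs 55.0% | 11.6% | 3.9% |
| 15% vs 25% | 50% | 57.5% vs 62.5% | 8.7% | 3.8% |
| 10% vs 30% | 30% | 37.0% vs 51.0% | 47.3% | 4.1% |
| 10% vs 30% | 40% | 46.0% vs 58.0% | 36.2% | 4.1% |
| 10% vs 30% | 50% | 55.0% vs 65.0% | 25.8% | 3.8% |

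In the excluded column the denominators are 100 x (1 - *c*), for example 85 and 75. With equal unresponsiveness the printed rule does not inflate the rejection rate; it only raises the reported rate in both arms.

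**Step 4. Deaths and ICU discharges.** Protocol 6.2.4 sets no delirium denominator. Protocol 6.2.3 says other binary outcomes are handled like renal failure, but the death rule for renal failure (6.2.2) turns on KDIGO status and cannot be carried over. The choice matters. Assume 10% dead in each arm, 40% versus 30% out of the ICU, and 50% delirium among those remaining. Counting absent patients as free of delirium gives 25% versus 30% and 9.4% rejection. Using assessed patients only (50 versus 60) gives 50% versus 50% and 3.5% rejection.

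**The case against.** The strongest reply is that Appendix 2 is a one-page worksheet and not the whole instrument. Protocol 5.3.1 cites the CAM-ICU as a published system, the worksheet mentions a training manual, and the online CRF and data dictionary are not among the documents. Trained staff may never run a squeeze test on a comatose patient, and the CRF may already offer an unable-to-assess entry. This stands as a limit: what sites actually do cannot be established from the documents. It does not remove the point. The manual is cited only for alternate pictures and questions, the printed rule has no such exit, and even if the CRF had one, 6.2.4 would not say how to analyse it.

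A reader might infer more than the documents support:

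- *That every unresponsive patient scores positive.* Feature 1 is also required, though most patients with septic shock who become unresponsive would meet it.
- *That the outcome simply measures sedation, coma and who is still in the ICU.* Responsive patients are still tested for attention and thinking, so delirium is mixed with these states, not replaced by them.
- *That participants who die or leave the ICU have no score.* The documents do not say so, and at daily CAM-ICU sites earlier assessments may exist. The absence of a rule for death and discharge is, on its own, missing detail.

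It is also fair to say that the rates in the table are invented, and that bias needs a difference between arms in unresponsiveness.

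**Conclusion.** The point holds in limited form. Applied as printed, the worksheet classifies a newly comatose or deeply sedated, unresponsive patient as having delirium and offers no alternative result. If unresponsiveness differs by arm, the Fisher comparison can reflect that difference.

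The size rests entirely on assumption. With 15% versus 25% unresponsive and equal delirium of 30-50% among responsive patients, the scored rates differ by 5 to 7 points and the test rejects about 9-14% of the time, against about 4% with such patients excluded. With 10% versus 30% unresponsive it rejects about 26-47%. With equal shares there is no inflation.

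The documents do not support saying that the trial's delirium result will be wrong, or that sites will score coma as delirium. Delirium is an additional secondary outcome with no power claim attached, and the primary and key secondary outcomes are unaffected. This is a minor point, worth correcting because the correction is cheap.

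**What to change.** 1. In 5.3.1 and Appendix 2, add a third result, coma / not assessable, for patients who do not respond to voice, identified from the RASS already on the form. Do not score them as CAM-ICU positive.
2. In 6.2.4, state that Fisher's exact test is applied among participants who could be assessed.
3. In the same paragraph, commit to reporting by arm the numbers dead, discharged from the ICU and not assessable.

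The cost is at most one extra CRF response option and a few sentences; no new assessments are needed. The downside is a smaller denominator and a comparison conditional on being alive, in the ICU and testable, so it has to be read alongside those counts.

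An ordered composite of delirium, coma and death should not become the main analysis. Take an assumed case per 100 in each arm: treated 10 dead, 30 out of the ICU, 15 unresponsive, 45 testable; placebo 20, 20, 25 and 35; delirium 40% of testable patients in both arms.

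- Best category (negative or discharged): 30 + 27 = 57 versus 20 + 21 = 41.
- Middle category (positive): 18 versus 14.
- Worst category (coma or dead): 15 + 10 = 25 versus 25 + 20 = 45.

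The Wilcoxon test on these counts gives p = 0.006. In simulation from these proportions it rejects about 79% of the time, against about 18% for the worksheet with Fisher's test and about 4% for Fisher's test among testable patients. That composite answers a different question and would let death, coma and discharge dominate the result.

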1  
2  
3  
4  
5  
6  
7  
8  
9  
10  
11  
12  
13  
14  
15  
16  
17  
18  
19  
20  
21  
22  
23  
24  
25  
26  
27  
28  
29  
30  
31  
32  
33  
34  
35  
36  
37  
38  
39  
40  
41  
42  
43  
44

172 **SYNOPSIS**

173

174 The “Ascorbic Acid, Corticosteroids, and Thiamine in Sepsis (ACTS)” trial is a multi-center, double-  
175 blind, randomized clinical trial that aims to determine the impact of Vitamin C, Hydrocortisone, and  
176 Vitamin B1 vs. Placebo on organ injury and mortality on participants with sepsis and septic shock.

177 The trial will be conducted in accordance with all applicable national and international laws,  
178 regulations, and guidelines The trial and this protocol is developed in accordance with the  
179 International Conference on Harmonization (ICH) guidelines and the Standard Protocol Items:  
180 Recommendations for Interventional Trials (SPIRIT) statement. The principal investigator wrote  
181 the protocol with input from the steering committee. Any substantial changes or amendments to the  
182 protocol will be clearly documented and communicated to all relevant parties.

183

**Title** Vitamin C, Hydrocortisone, and Vitamin B1 in Sepsis and Septic Shock – A Randomized, Double-Blind, Placebo-Controlled Trial (The ACTS Trial)

Clinical Trials Number	NCT03389555
Sources of monetary or material support	Open Philanthropy Project ( https://www.openphilanthropy.org/ )
Study Sites	12-sites in the United States
Condition studied	Sepsis and septic shock
Interventions	Vitamin C (1.5g every 6 hours x 4-days), hydrocortisone (50mg every 6 hours x 4-days), and Vitamin B1 (100mg every 6 hours x 4-days)
Comparator	Placebo
Inclusion criteria	
 
• Adult participant (age <math>\geq</math> 18 years)
 
• Suspected (cultures drawn and antibiotic given) or confirmed (via culture results) infection
 
• Receiving vasopressor (norepinephrine, phenylephrine, epinephrine, dopamine, vasopressin, or angiotensin II)
 

Exclusion criteria	
 
• Member of a protected population (pregnant, prisoner)
 
• Known history of kidney stones within the past 1 year
 
• End stage renal disease (ESRD) requiring dialysis
 
• Known history of G6PD deficiency
 
• Known history of Hemochromatosis
 
• Comfort Measures Only status
 
• Anticipated death within 24-hours despite maximal therapy (as determined by the enrolling physician)
 
• Receiving supplemental vitamin B1 in a dose greater than that contained in a multivitamin (<2mg)
 
• Clinical indication for steroids (e.g. chronic use) as determined by the clinical team providing this drug
 
• Clinical indication for ascorbic acid supplementation in any form
 
• Clinical indication for vitamin B1 as determined by the clinical team providing this drug
 
• Known allergy to vitamin C, hydrocortisone, or vitamin B1
 

Study type	Interventional Allocation: Randomized (1:1) Intervention model: Parallel group Masking: Double-blind
Target sample size	200 Participants (100/arm)
Primary outcome	Change in the Sequential Organ Failure Assessment (SOFA) score between enrollment and 72-hours
Key secondary outcomes	Incidence of renal failure during index ICU stay 30-day mortality

186 **STEERING COMMITTEE**

187

235 limited, if any, success. Recently, three large studies found no benefit from early goal directed  
236 therapy over usual care in emergency department participants with sepsis. Other recent studies  
237 focusing on hemodynamics, fluid therapy, and transfusions have also failed to show a significant  
238 benefit in this participant population. Previous studies focusing on immunomodulatory therapies or  
239 drotrecogin alfa have likewise shown disappointing results.

240

241 **1.3 The combination of vitamin C, hydrocortisone, and vitamin B1 may improve outcomes**

242 In a before-and-after study exploring the effects of the combination of vitamin C, hydrocortisone, and  
243 vitamin B1 in a cohort of participants with sepsis and septic shock, Marik et. al. found a remarkable  
244 improvement in time to shock reversal ( $18.3 \pm 9.8$  hours vs.  $54.9 \pm 28.4$  hours), organ injury ( $\Delta$ SOFA  
245  $4.8 \pm 2.4$  vs.  $0.9 \pm 2.7$ ), and mortality (8.5% vs. 40.4%) following implementation of the drug 'cocktail'  
246 as compared to before implementation even after adjusting for potential confounders. This study  
247 joins other promising trials of individual elements of this drug combination. In a trial of vitamin B1 in  
248 septic shock, there was a substantial reduction in mortality and organ injury (particularly kidney  
249 injury) in those with vitamin B1 deficiency and septic shock who were given vitamin B1 as compared  
250 to placebo. In addition, several studies of vitamin C alone have shown promise in critically ill  
251 populations and a recent meta-analysis of corticosteroids in sepsis suggests potential benefit.

252

253 **1.4 Physiologic Rationale**

254 The combination of vitamin C, hydrocortisone, and vitamin B1 is hypothesized to improve outcomes  
255 in sepsis through a number of mechanisms. Vitamin C is an important contributor to endothelial  
256 integrity and severe deficiency states (e.g. scurvy) can result in endothelial breakdown with resultant  
257 vascular leak and edema. In addition, vitamin C is a potent anti-oxidant and is integral to  
258 endogenous vasopressor synthesis. Hydrocortisone, a potential adjunctive therapy in septic  
259 shock, may act synergistically with vitamin C. Vitamin B1, a key cofactor of pyruvate  
260 dehydrogenase, is a critical component of metabolic dysfunction without which a shift towards  
261 anaerobic energy production occurs. Vitamin B1 is also a necessary component of the pentose  
262 phosphate pathway, which plays a role in reducing oxidative stress. While the physiologic effects  
263 of these drugs given in combination is not entirely known, we hypothesize that there will be  
264 synergistic effects with respect the metabolic resuscitation of sepsis.

265 **2. TRIAL DESIGN**

266 **2.1 Overview**

267 This will be an investigator-initiated, multicenter, randomized, placebo-controlled, parallel group,  
268 double-blind, superiority trial of vitamin C, hydrocortisone, and vitamin B1 vs. placebo in participants  
269 with sepsis and septic shock. A total of 200 adult participants will be enrolled. The primary outcome  
270 will be the change in SOFA score between enrollment and 72-hours. Key secondary outcomes  
271 include the incidence of renal failure during the index ICU stay and survival at 30 days.

272

273 **2.2 Allocation**

274 Participants will be randomized in a 1:1 ratio to either the combination of vitamin C, hydrocortisone,  
275 and vitamin B1 or placebo in blocks with random sizes of 2 or 4. The randomization will be stratified  
276 according to site. An independent statistician will create the randomization list using a random  
277 number generator. The complete list will only be shared with an independent pharmacy consultant,  
278 who will not be involved in clinical care. The pharmacy consultant and the independent statistician  
279 will both store the randomization list. The research pharmacy at each enrolling site will receive a  
280 site-specific randomization list.

281

282 **2.3 Intervention**

283 *2.3.1 Vitamin C, Hydrocortisone, and Vitamin B1*

284 The study drugs will consist of vitamin C (1.5g every 6 hours x 4-days), hydrocortisone (50mg every 6  
285 hours x 4-days), and vitamin B1 (100mg every 6 hours x 4-days).

286

287 *2.3.2 Placebo*

288 The placebo will consist of matching volumes of normal saline (0.9% NaCl). See below section 4.4  
289 for specifics of drug and placebo preparation.

290

291 **2.4 Blinding**

292 The trial will be double-blind; participants, investigators, and the clinical team will be blinded to the  
293 allocation. Only the pharmacy providing the study drug will be aware of the allocation. The  
294 pharmacy will not be involved with clinical care or outcome evaluation.

295

296 As vitamin C possess a yellow tinge, the bags containing the vitamin C/placebo will be covered with  
297 light-protective bags. In testing, after dilution there is not distinguishing characteristics of the vitamin  
298 C vs. placebo in the IV tubing. Vitamin C, hydrocortisone, and vitamin B1 are not known to have  
299 distinctive rapid effects which could lead to unblinding.

300

301 The decision to unblind will be at the complete discretion of the treating physician and clinical team.  
302 If a clinical team wishes to unblind a participant (e.g. if anaphylaxis occurs), they will contact the  
303 research pharmacy who will reveal the study group to the clinical team (but the research team will  
304 remain blinded). However, we do not expect many scenarios where emergency unblinding will be  
305 necessary. In case unblinding occurs, the reason(s) will be clearly documented in the case report  
306 form. The patient will no longer receive study medications, but will be followed for outcomes.

307

308 **2.5 Regulatory Issues**

309 An Investigational New Drug (IND) application was submitted to and approved by the Food and  
310 Drug Administration (FDA) for the study of vitamin C, hydrocortisone, and vitamin B1 in sepsis and  
311 septic shock (IND # 136882).

312

313 The trial has been registered on ClinicalTrials.gov: NCT03389555

314

315

316 **3. SETTING AND PARTICIPANT POPULATION**

317 **3.1 Setting**

318 The trial will be conducted at approximately 13 hospitals in the United States. Additional sites might  
319 be recruited if needed.

320

321 **3.2 Inclusion criteria**

322 Inclusion criteria:

- 323 1) Adult participant (age  $\geq$  18 years)  
324 2) Suspected (cultures drawn and antibiotic given) or confirmed (via culture results) infection  
325 3) Receiving (continuous infusion) vasopressor (norepinephrine, phenylephrine, epinephrine,  
326 dopamine, angiotensin II, or vasopressin)  
327 a. Hypotension related primarily to sepsis as opposed to another cause of hypotension  
328 (e.g. bleed, cardiogenic shock)

329

330 **3.3 Exclusion criteria**

331 Exclusion criteria:

- 332 1) Member of a protected population (pregnant, prisoner)  
333 2) Known history of kidney stones within the past 1 year (not including incidentally noted stones  
334 noted on imaging studies)  
335 3) End stage renal disease requiring dialysis (hemodialysis or peritoneal dialysis)  
336 4) Known history of G6PD deficiency  
337 5) Known history of Hemochromatosis  
338 6) Comfort Measures Only status  
339 7) Anticipated death within 24-hours despite maximal therapy (as determined by the enrolling  
340 physician)  
341 8) Receiving supplemental vitamin B1 in a dose greater than that contained in a multivitamin  
342 (<2mg)  
343 9) Clinical indication for steroids (e.g. chronic use) as determined by the clinical team providing  
344 this drug  
345 10) Clinical indication for ascorbic acid supplementation in any form  
346 11) Clinical indication for vitamin B1 as determined by the clinical team providing this drug  
347 12) Known allergy to vitamin C, hydrocortisone, or vitamin B1

348

349 Justification of Inclusion and Exclusion Criteria: The inclusion criteria were chosen to isolate a septic  
350 participant population with high risk of organ injury and death. The exclusion criteria were chosen to  
351 minimize the risk of potential harm and to ensure that participants enrolled do not already have  
352 chronic end-stage renal failure with a high likelihood of early need for renal replacement therapy. By  
353 evaluating this high-risk population (i.e., most likely to die), we will target those most likely to benefit  
354 and therefore increase the probability of showing efficacy.

355

356 **3.4 Pregnancy**

357 Hydrocortisone is considered pregnancy class C on the basis of animal studies showing an  
358 association between prenatal parenteral hydrocortisone use and risk of cleft-palate. In addition,  
359 there are concerns about effects of hydrocortisone on fetal growth and the possibility of neonatal  
360 adrenal insufficiency. The effects of high-dose vitamin C and thiamine in pregnancy are not entirely  
361 known. As such, participants who are pregnant will be excluded from the study. Prior to enrollment,  
362 all participants of potentially child-bearing potential (women aged <45 years) will be required to  
363 have a negative serum or urine HCG test (generally performed as standard-of-care).

364

365 We will additionally inform all women of child-bearing potential who are randomized in this study  
366 that we recommend they remain abstinent or use two forms of birth control during the study period  
367 and for a period of 48-hours after the last dose of study drug.

368

